5.12.4.2. Systemic Hypersensitivity Reaction

The number and proportion of patients experiencing treatment-emergent potential systemic hypersensitivity reactions will be summarized and compared by treatment group using Fisher's exact test. The following MedDRA Standardized MedDRA Query (SMQ) will be used to identify potential systemic hypersensitivity reactions from all TEAEs:

- Anaphylactic reaction (SMQ). Besides using the narrow and broad terms designated within the SMQ, the following search algorithm will also be implemented as another approach to determine if a patient had an anaphylactic reaction: if a patient (had at least 1 event in Category A) or (had at least 1 event that is in Category B and also had at least 1 event that is in Category C) or (had at least 1 event that is in Category D and [also had at least 1 event in Category B or at least 1 event in Category C])
- Angioedema (SMQ)
- Hypersensitivity (SMQ)

Specifically, need to perform the following: (1) any narrow or algorithmic term from any 1 of the 3 SMQs indicated above (ie, combined search across narrow and algorithmic portions of all 3 SMQs); (2) any narrow scope term within each SMQ, separately (ie, narrow SMQ search); (3) any term within each SMQ, separately (ie, broad SMQ search); (4) narrow scope term search within each SMQ, report the PT nested within each SMQ.

A similar summary will be provided for the TEAE related to study drug judged by the investigator.

Note that an individual patient may contribute multiple events. Also, a single event may satisfy multiple SMQs, in which case the event contributes to every applicable SMQ.

5.12.4.3. Injection Site Reaction

The injection site reactions will be searched by MedDRA PTs from all TEAEs. The number and percentage of patients experiencing treatment-emergent injection site reactions will be summarized and compared by treatment group using Fisher's exact test.

For injection site reactions, the presence and severity of erythema, induration, pain, pruritus, and edema will be collected through the eCRF and will be summarized for each treatment. There will be no statistical comparison between treatments.

5.12.4.4. Hepatobiliary Events

5.12.4.4.1. *Treatment-Emergent Potential Hepatic Disorder*

The percentages of patients with treatment-emergent drug-related hepatic disorder events will be summarized and compared by treatment group using MedDRA PT nested within each SMQ ordered by decreasing frequency. The following SMQs based on MedDRA will be used to identify potential hepatic disorders:

- Broad and narrow terms in the Liver-related investigations, signs, and symptoms SMQ (20000008)

- Broad and narrow terms in the Cholestasis and jaundice of hepatic origin SMQ (20000009)
- Broad and narrow terms in the Hepatitis non-infections SMQ (20000010)
- Broad and narrow terms in the Hepatic failure, fibrosis and cirrhosis and other liver damage SMQ (20000013)
- Narrow terms in the Liver-related coagulation and bleeding disturbances SMQ (20000015)

The percentage of patients with any 1 of the terms will be summarized in addition to the percentages for each MedDRA PT. The percentages of patients with potentially drug-related hepatic disorders that led to permanent study treatment discontinuation will be summarized similarly.

5.12.4.4.2. Liver Enzyme Lab Values

The liver enzyme measures (alanine aminotransferase [ALT], aspartate aminotransferase [AST], alkaline phosphatase [ALP], direct bilirubin, total bilirubin) will be summarized by treatment group. Postbaseline value and the change from baseline (last nonmissing value before randomization) to postbaseline value at Week 26 visit (planned test) will be summarized for patients who have both a baseline and at least 1 postbaseline result, and compared between treatment groups by using ANCOVA model with the term of treatment and baseline value of the response variable. All analyses will be provided in both CN and SI units.

The last nonmissing observation at or prior to Week 26 (including early discontinuation visit) will also be analyzed by an ANCOVA model with the term of treatment, baseline value of response variable.

5.12.4.4.3. Treatment-Emergent Elevation of Liver Enzyme Lab Values

The percentages of patients with the following elevations in hepatic laboratory tests at any time during the treatment period (0-26 weeks) will be summarized between treatment groups:

- The percentages of patients with postbaseline ALT measurement greater than or equal to 3 times (3X), 5 times (5X), and 10 times (10X) the Covance upper limit of normal (ULN) will be summarized for all patients with a postbaseline value and for the following subcategories based on baseline value
 - The analysis of 3X ULN will contain 4 subcategories:
 - patients whose non-missing maximum baseline value is less than or equal to 1X ULN
 - patients whose maximum baseline value is greater than 1X ULN but less than 3X ULN
 - patients whose maximum baseline value is greater than or equal 3X ULN
 - patients whose baseline values are missing

- The analysis of 5X ULN will be contain 5 subcategories:
 - patients whose non-missing maximum baseline value is less than or equal to 1X ULN
 - patients whose maximum baseline value is greater than 1X ULN but less than 3X ULN
 - patients whose maximum baseline value is greater than or equal to 3X ULN but less than 5X ULN
 - patients whose maximum baseline value is greater than or equal to 5X ULN
 - patients whose baseline values are missing
- The analysis of 10X ULN will contain 6 subcategories:
 - patients whose non-missing maximum baseline value is less than or equal to 1X ULN
 - patients whose maximum baseline value is greater than 1X ULN but less than 3X ULN
 - patients whose maximum baseline value is greater than or equal to 3X ULN but less than 5X ULN
 - patients whose maximum baseline value is greater than or equal to 5X ULN but less than 10X ULN
 - patients whose maximum baseline value is greater than or equal to 10X ULN
 - patients whose baseline values are missing
- The percentages of patients with postbaseline AST measurement greater than or equal to 3X, 5X, and 10X the Covance ULN will be summarized for all patients with a postbaseline value and for subcategories based on baseline, as described above for ALT.
- The percentages of patients with post-baseline total bilirubin measurement greater than or equal to 2 times (2X) the Covance ULN will be summarized for all patients with a post-baseline value and the following 4 subcategories:
 - patients whose non-missing maximum baseline value is less than or equal to 1X ULN
 - patients whose maximum baseline value is greater than 1X ULN but less than 2X ULN
 - patients whose maximum baseline value is greater than or equal to 2X ULN
 - patients whose baseline values are missing

Baseline will be the maximum observation in the baseline period. The maximum value will be the maximum value from the treatment period. Planned and unplanned tests will be included.

Graphical profiles of ALT, AST, total bilirubin, and ALP will be provided for patients with an ALT or AST $\geq 3X$ ULN or total bilirubin $\geq 2X$ ULN during the treatment period. A listing for these patients will also be provided, including the actual measurement of ALT, AST, ALP, and total bilirubin, the corresponding reference high limits, demographics, disposition, drug exposure, and AEs. The review for these patients includes an assessment of the proximity of any ALT or AST elevation to any total bilirubin elevation, ALP levels, other potential causes, and the temporal association with events such as nausea, vomiting, anorexia, abdominal pain, or fatigue.

All patient data, regardless of whether on IP, will be used for the above analyses related to hepatobiliary events.

5.12.5. Clinical Laboratory Evaluation

The data from safety laboratory measures will be summarized at Week 26 where the lab test is planned to be collected. Postbaseline and change from baseline to postbaseline for laboratory tests will be summarized for patients who have both baseline and at least 1 postbaseline result and compared between treatment groups by using ANCOVA model with the term of treatment and baseline value of the response variable. Analyses will be provided in both SI and CN units.

The last nonmissing observation at or prior to Week 26 (planned tests including early discontinuation) will also be analyzed by an ANCOVA model with the term of treatment, baseline value of the response variable.

The percentages of patients with treatment-emergent abnormal, high, or low laboratory results at any time during the treatment period (0 to 26 weeks) will be summarized for patients who have both baseline and at least 1 postbaseline result and compared between treatment groups using Fisher's exact tests. A treatment-emergent abnormal result is defined as a change from normal at all baseline visits to abnormal at any time during the treatment period. A treatment-emergent high result is defined as a change from a value less than or equal to the high limit at all baseline visits to a value greater than the high limit at any time during the treatment period. A treatment-emergent low result is defined as a change from a value greater than or equal to the low limit at all baseline visits to a value less than the low limit at any time during the treatment period. Planned and unplanned measurements will be included. Covance reference ranges will generally be used to define the low and high limits. Only patients who have normal baseline values for the lab being performed will be included in the analysis for treatment-emergence.

Liver enzymes measures will not be included in the above analyses as different analyses will be used as described in Section 5.12.4.4.2 and Section 5.12.4.4.3.

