#### 8.1.1. Permanent Discontinuation from Study Treatment

Possible reasons leading to permanent discontinuation of IP are:

- **Subject Decision**
  - The patient/or the patient's designee, for example, parents or legal guardian requests to discontinue IP.
- The investigator may decide that the patient should stop IP. If this decision is made because of an AE, SAE, or a clinically significant laboratory value, the study drug is discontinued for that patient and appropriate measures are to be taken. Lilly or its designee is to be alerted.
- The patient becomes pregnant.
- An investigator, study site personnel performing assessments, or patient is unblinded, the patient must discontinue IP.
- The patient, for any reason, requires treatment with another therapeutic regimen or therapeutic agent that has been demonstrated to be effective for treatment of the study indication with the exception of those described in Section 7.7. Discontinuation from IP should occur prior to introduction of the new agent.
- Frequent use of prohibited concomitant medication, see Section 7.7.
- Patient has not taken IP for more than 14 consecutive days.
- Patient discontinuation is recommended by the DMC.
- **Discontinuation due to a hepatic event or liver test abnormality.** Patients who are discontinued from the IP due to a hepatic event or liver test abnormality should have additional hepatic safety data collected via case report form (CRF).

Discontinuation of the IP for abnormal liver tests **should be** considered by the investigator when a patient meets 1 of the following conditions after consultation with the Lilly-designated medical monitor:

- ALT or AST  $>8\times$ ULN
- ALT or AST  $>5\times$ ULN for more than 2 weeks
- ALT or AST  $>3\times$ ULN and total bilirubin level (TBL)  $>2\times$ ULN or international normalized ratio  $>1.5$
- ALT or AST  $>3\times$ ULN with the appearance of fatigue, nausea, vomiting, right upper quadrant pain or tenderness, fever, rash, and/or eosinophilia ( $>5\%$ )
- alkaline phosphatase (ALP)  $>3\times$ ULN
- ALP  $>2.5\times$ ULN and TBL  $>2\times$ ULN
- ALP  $>2.5\times$ ULN with the appearance of fatigue, nausea, vomiting, right quadrant pain or tenderness, fever, rash, and/or eosinophilia ( $>5\%$ )

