##### **Hepatic Safety Data Collection**

Additional safety data should be collected via the CRF if 1 or more of the following conditions occur:

- elevation of serum ALT to  $\geq 5 \times ULN$  on 2 or more consecutive blood tests
- elevated serum TBL to  $\geq 2 \times ULN$  (except for cases of known Gilbert's syndrome)
- elevation of serum ALP to  $\geq 2 \times ULN$  on 2 or more consecutive blood tests
- patient discontinued from treatment due to a hepatic event or abnormality of liver tests

- hepatic event considered to be a SAE.

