### Hepatic Monitoring Tests

Hepatic Hematologya	Haptoglobina
Hemoglobin	
Hematocrit	Hepatic Coagulationa
RBC	Prothrombin Time
WBC	Prothrombin Time, INR
Neutrophils, segmented	
Lymphocytes	Hepatic Serologiesa,b
Monocytes	Hepatitis A antibody, total
Eosinophils	Hepatitis A antibody, IgM
Basophils	Hepatitis B surface antigen
Platelets	Hepatitis B surface antibody
	Hepatitis B Core antibody
Hepatic Chemistrya	Hepatitis C antibody
Total bilirubin	Hepatitis E antibody, IgG
Direct bilirubin	Hepatitis E antibody, IgM
Alkaline phosphatase	
ALT	Anti-Nuclear Antibodya
AST	
GGT	Alkaline Phosphatase Isoenzymesa
CPK	
	Anti-Smooth Muscle Antibody (or Anti-Actin Antibody)a

Abbreviations: ALT = alanine aminotransferase; AST = aspartate aminotransferase; CPK = creatine phosphokinase; GGT = gamma-glutamyl transferase; Ig = immunoglobulin; INR = international normalized ratio; RBC = red blood cells; WBC = white blood cells.

a Assayed by Lilly-designated or local laboratory.

b Reflex/confirmation dependent on regulatory requirements and/or testing availability.

---

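### The SAP removes ALP and direct bilirubin from the treatment-emergent laboratory analysis without a categorical replacement, so four protocol ALP rules can be met with no entry in any elevation table, profile or hepatic listing

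*SAP*

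**What the plan says.** SAP 5.12.4.4.2 defines the group of measures: "The liver enzyme measures (alanine aminotransferase [ALT], aspartate aminotransferase [AST], alkaline phosphatase [ALP], direct bilirubin, total bilirubin) will be summarized by treatment group". For these five it plans summaries of the Week 26 value and change, an ANCOVA, and an ANCOVA of the last non-missing value up to Week 26, including the early discontinuation visit.

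SAP 5.12.5 plans treatment-emergent abnormal, high and low analyses for safety laboratory tests, then excludes the liver group: "Liver enzymes measures will not be included in the above analyses as different analyses will be used as described in" Sections 5.12.4.4.2 and 5.12.4.4.3.

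SAP 5.12.4.4.3 tabulates ALT and AST at 3x, 5x and 10x ULN and total bilirubin at 2x ULN, by baseline category, counting planned and unplanned tests. It continues: "Graphical profiles of ALT, AST, total bilirubin, and ALP will be provided for patients with an ALT or AST" at or above 3x ULN, or total bilirubin at or above 2x ULN. The listing covers the same patients.

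The protocol uses ALP in its own right. Section 9.4.6.1 calls for a liver retest at ALP at or above 2x ULN. Its subsection on hepatic data collection asks for added CRF data on "elevation of serum ALP to" at least 2x ULN on two or more consecutive tests. Section 8.1.1 says that "Discontinuation of the IP for abnormal liver tests" should be considered under seven conditions, three of which involve ALP: above 3x ULN; above 2.5x ULN with total bilirubin above 2x ULN; and above 2.5x ULN with symptoms.

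**The concern.** The exclusion in 5.12.5 is justified by replacement analyses. For ALT, AST and total bilirubin the replacement exists. For ALP and direct bilirubin it does not: they leave one categorical analysis and never enter the other. Because the stated reason is that other analyses take over, this reads as an oversight rather than a choice.

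What is at stake is the hepatic laboratory safety report. The protocol asks sites to act on ALP alone, yet the SAP would give no count, by arm, of patients who reached the ALP levels that prompt that action, and no listing of who they were. An imbalance in ALP elevations between arms could go uncounted.

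**Working it through.** The plan states no figure here, so the check is one of coverage: does meeting each protocol rule guarantee entry into a 5.12.4.4.3 output?

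**Inputs.** The rules are the seven conditions in Protocol 8.1.1 and, from 9.4.6.1, three retest triggers and three laboratory data-collection triggers: 7 + 3 + 3 = 13. The SAP entry condition, in multiples of ULN, is E: ALT ≥3, or AST ≥3, or total bilirubin (TBL) ≥2.

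| Protocol rule (multiples of ULN) | Use | Does it imply E? |
|---|---|---|
| ALT or AST >8 | consider stopping IP | yes |
| ALT or AST >5 for over 2 weeks | consider stopping IP | yes |
| ALT or AST >3 with TBL >2 or INR >1.5 | consider stopping IP | yes |
| ALT or AST >3 with symptoms | consider stopping IP | yes |
| ALP >3 | consider stopping IP | **no** |
| ALP >2.5 with TBL >2 | consider stopping IP | yes, through TBL |
| ALP >2.5 with symptoms | consider stopping IP | **no** |
| ALT ≥3 | retest | yes |
| ALP ≥2 | retest | **no** |
| TBL ≥2 | retest | yes |
| ALT ≥5, consecutive tests | data collection | yes |
| TBL ≥2 | data collection | yes |
| ALP ≥2, consecutive tests | data collection | **no** |

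Nine rules always lead to an output and 13 − 9 = 4 need not. All four are ALP rules. An enumeration over a grid of ALT, AST, ALP and TBL multiples, with symptoms, persistence and INR switched on and off, gave the same split. Example: ALP 3.2x ULN with ALT and AST below 3x and TBL below 2x meets the >3x and ≥2x rules and enters nothing in 5.12.4.4.3.

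**Could another part of the SAP fill the gap?** Table ITSB.5.2 has a general row for categorical analysis of chemistry, but it sets population, baseline and visits, and the specific text of 5.12.5 takes the liver measures out.

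**What do the continuous summaries cover?** The Schedule of Activities places postbaseline chemistry only at Visit 15 and early discontinuation, so the two analyses in 5.12.4.4.2 reach the planned postbaseline ALP tests. The retest required by Protocol 9.4.6.1 within 3 to 5 days is unplanned. Section 5.12.4.4.3 counts unplanned tests for its three tabulated measures, whereas 5.12.4.4.2 and Table ITSB.5.2 confine the continuous analyses to planned tests. Unplanned ALP results are therefore not tabulated.

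**Would one added condition close the gap?** Let E′ be E or ALP ≥2. Each of the four open rules requires ALP of at least 2x ULN (≥2, ≥2 on consecutive tests, >2.5, >3), so each implies E′. Coverage becomes 13 of 13.

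**The case against.** The best defence is that ALP is not ignored. SAP 5.1 requires SD, median, minimum and maximum for continuous measures, for actual values and for change. The highest planned ALP in each arm is therefore reported, and it would be wrong to infer that only means are shown. This stands, but a maximum describes one patient per arm, in laboratory units. It gives neither a multiple of ULN nor a number of patients, and it omits unplanned tests.

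Second, a patient with raised ALP alone can surface elsewhere: in the hepatic SMQ tables of 5.12.4.4.1, the discontinuation listing of 5.6, the adverse event discontinuation outputs of 5.12.2, or a narrative under 5.12.8. A reader might infer that such a patient is absent from every safety output; the documents do not support that. But these routes need a reported adverse event or a stop of IP, and Protocol 9.4.4 makes a laboratory finding an adverse event only when it is clinically significant and results in a diagnosis. They do not depend on the ALP value.

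Third, the SAP measures elevations against the Covance ULN, while Protocol Appendix 4 allows hepatic monitoring tests to be "Assayed by Lilly-designated or local laboratory". A reader might infer that local results will be divided by the wrong limit. Neither document says so. The local-laboratory rule in SAP 5.11.1 concerns HbA1c, and the hepatic listing shows the corresponding reference limits. That inference forms no part of this point.

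**Conclusion.** The point holds for categorical analysis of laboratory values. Two of the five liver measures, ALP and direct bilirubin, have none, and four of the protocol's 13 hepatic laboratory rules can be met without entry in an elevation table, profile or hepatic listing. Among the seven conditions for considering discontinuation of IP, two can escape; the third ALP condition is caught through total bilirubin.

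Two stronger readings go too far. A reader might take the ALP levels in Protocol 8.1.1 as mandatory stopping thresholds, but the text asks the investigator to consider stopping after consulting the medical monitor. A reader might also extend the mismatch with the protocol to direct bilirubin, but the protocol sets no threshold for it; that gap is internal to the SAP.

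The conclusion rests on reading the specific exclusion in 5.12.5 as overriding the general row in Table ITSB.5.2. It says nothing about how many patients will be affected, which the documents do not allow one to estimate, and it does not judge the clinical thresholds. No primary or gated conclusion changes. It is still worth correcting, because a stated exclusion creates the gap and the data are already collected.

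**What to change.** Three changes to the SAP:

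- In 5.12.4.4.3, add ALP rows at thresholds already in the protocol (at or above 2x and above 3x ULN), by baseline category, counting planned and unplanned tests and using age- and sex-appropriate reference limits.
- Add ALP at or above 2x ULN to the entry condition for the profiles and listing.
- In 5.12.5, keep direct bilirubin in the treatment-emergent high analysis, so that the exclusion covers only measures with a replacement categorical analysis.

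The cost is SAP wording and a few table rows. There are no new samples or visits, and no clinical rule changes. The drawback is that some ALP flags in growing children will be physiological; the baseline categories, appropriate reference limits and comparison between arms help to put those in context.

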5.12.6. Vital Signs and Other Physical Findings

Postbaseline measurements and change from baseline to post-baseline for vital signs and physical characteristics (systolic blood pressure, diastolic blood pressure, pulse rate, height, weight, BMI) at the scheduled visits will be summarized for patients who have both baseline and at least 1 postbaseline result.

The measurements during the treatment period (0 to 26 weeks) will be analyzed by an MMRM model with treatment, baseline value of the response variable, visit, and visit by treatment interaction as fixed factors and patient as the random factor.

An ANCOVA model will also be used for the analysis of the last nonmissing observation (planned measurements including early discontinuation) during the treatment period. The ANCOVA models are the same as those used for clinical laboratory measures.

The percentages of patients with treatment-emergent high or low vital signs at any time during the treatment period (0 to 26 weeks) will be summarized by treatment group for patients who have both baseline and at least 1 postbaseline measurement. A treatment-emergent high result is defined as a change from a value not meeting criteria for the high limit during the baseline period to a value meeting the criteria for the high limit at any time that meets the specified change amount during the treatment period. A treatment-emergent low result is defined as a change from a value not meeting criteria for the low limit during the baseline period to a value meeting the criteria for the low limit at any time that meets the specified change amount during the treatment period. Treatment comparison will be based on Fisher's exact test. [Table ITSB.5.5](#) will be used to define the low and high limits and change thresholds.

Table ITSB.5.5. Categorical Criteria for Abnormal Treatment-Emergent Blood Pressure and Pulse Measurement for Children and Adolescents

Age (years)		Systolic BP, mm Hg (Supine or sitting – forearm at heart level)	Diastolic BP, mm Hg (Supine or sitting – forearm at heart level)	Pulse/HR, bpm (Supine or sitting)
Infant <2	Low	≤70 and decrease ≥15	≤35 and decrease ≥10	<70 and decrease ≥25
	High	≥112 and increase ≥15	≥74 and increase ≥10	>190 and increase ≥25
Child 2-4	Low	≤75 and decrease ≥15	≤40 and decrease ≥10	<60 and decrease ≥25
	High	≥116 and increase ≥15	≥76 and increase ≥10	>160 and increase ≥25
Child 5-9	Low	≤80 and decrease ≥15	≤45 and decrease ≥10	<60 and decrease ≥25
	High	≥122 and increase ≥15	≥78 and increase ≥10	>150 and increase ≥25
Child 10-11	Low	≤85 and decrease ≥20	≤50 and decrease ≥10	<60 and decrease ≥25
	High	≥126 and increase ≥20	≥82 and increase ≥10	>140 and increase ≥25
Adolescent 12-14	Low	≤90 and decrease ≥20	≤50 and decrease ≥10	<50 and decrease ≥15
	High	≥136 and increase ≥20	≥86 and increase ≥10	>120 and increase ≥15
Adolescent 15-17	Low	≤90 and decrease ≥20	≤50 and decrease ≥10	<50 and decrease ≥15
	High	≥140 and increase ≥20	≥90 and increase ≥10	>100 and increase ≥15

Abbreviations: BP = blood pressure; HR = heart rate.

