Unless otherwise noted, all tests of treatment effects will be conducted at a 2-sided alpha level of 0.05, and CIs will be calculated at 95%, 2-sided. All tests of interactions between treatment groups and other factors will be conducted at a 2-sided alpha level of 0.10. Countries in similar geographic regions with fewer than 10 patients, based on all randomized population, will be pooled to achieve a pooled country of at least 10 patients. All analyses using country in the model will use a pooled country, unless otherwise specified. The final pooling by country and geographic region will be finalized prior to data lock.

Baseline is defined as the last non-missing measurement at or before the randomization visit (Visit 4), unless otherwise specified.

A restricted maximum likelihood-based, mixed-effect model repeated-measure (MMRM) analysis will be used to analyze continuous longitudinal variables. All the longitudinal observations at each scheduled postbaseline visit will be included in the analysis. The model for

the analysis of the primary efficacy endpoint of change from baseline in HbA1c will include the fixed class effects of treatment, strata (pooled country, type of basal insulin, and age group), visit, and treatment-by-visit interaction, as well as the continuous, fixed covariate of baseline value. For analyses of variables other than HbA1c, the HbA1c stratum ( $\leq 8.0\%$ ,  $> 8.0\%$ ) will be included in the model. An unstructured covariance structure will be used to model the within-patient errors. Significance tests will be based on least-squares (LS) means and Type III tests. SAS PROC MIXED will be used to perform the analysis. If this analysis fails to converge, the following covariance structures will be tested, in order:

- Toeplitz with heterogeneity
- Autoregressive with heterogeneity
- Compound symmetry with heterogeneous variances
- Toeplitz
- Autoregressive
- Compound symmetry without heterogeneous variances.

The first covariance structure that converges will be used. The Kenward-Roger approximation will be used to estimate denominator degrees of freedom.

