#### **10.3.3.3. Tertiary/Exploratory Analyses**

Continuous variables and the change from baseline for these variables will be analyzed either by the MMRM or ANCOVA models described in Section 10.3.3.1. Categorical variables will be analyzed either by model (for example, logistic regression) or by Fisher's exact test or Pearson's chi-square test. Analysis details for the tertiary endpoints will be described in the SAP.

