4. To compare LY900014, LY900014 +20, and Humalog with respect to the incidence and rate of documented post-dose hypoglycemia	4. Rate (events/patient/year) and incidence (percent of patients with events) of documented post-dose hypoglycemic events within 1 and 2 hours after the prandial dose from Week 0 through Week 26
5. To compare LY900014, LY900014 +20, and Humalog with respect to the incidence and rate of documented hypoglycemia	5. Rate (events/patient/year) and incidence (percent of patients with events) of documented hypoglycemic events from Week 0 through Week 26
6. To compare LY900014, LY900014 +20, and Humalog on the rate of severe hypoglycemic events	6. Rate (events/patient/100 years) of severe hypoglycemic events from Week 0 through Week 26

Objectives and Endpoints

Objectives	Endpoints
7. To compare LY900014, LY900014 +20, and Humalog with respect to total, basal, and prandial insulin dose	7. Change from baseline in total, basal, and prandial insulin doses and prandial/total insulin dose ratios at Week 26
8. To compare LY900014, LY900014 +20, and Humalog with respect to the proportion of patients achieving HbA1c targets	8. The proportion of patients with HbA1c <7% and <7.5% at Week 26
9. To compare LY900014, LY900014+20, and Humalog with respect to 7-point SMBG	9. Change from baseline to Week 26 in 7-point SMBG values
Tertiary/Exploratory Objectives	
10. To compare LY900014, LY900014 +20, and Humalog with respect to changes in body weight	10. Change in weight (kg) from baseline to Week 26
11. To compare LY900014, LY900014 +20, and Humalog with respect to glycemic variability	11. Within-day and between-day glycemic variability measured by the standard deviation and the coefficient of variation of 7-point SMBG profiles
12. To compare the incidence of treatment-emergent positive anti-insulin lispro antibodies for LY900014, LY900014 +20, and insulin lispro	12. Incidence of treatment-emergent positive anti-insulin lispro antibodies

Abbreviations: HbA1c = hemoglobin A1c; NIM = noninferiority margin; SMBG = self-monitored blood glucose; T1D = type 1 diabetes.

5. A Priori Statistical Methods

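### The SAP models weight change in children without age group or the other randomization strata and does not say why; the cost is precision, not bias.

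*SAP*

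**What the plan says.** **Endpoint.** Objective 10 in SAP Table ITSB.4.1 (protocol Table ITSB.2 has the same) is "Change in weight (kg) from baseline to Week 26", listed as tertiary/exploratory.

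**SAP model.** Section 5.12.6 groups weight with the vital signs: "systolic blood pressure, diastolic blood pressure, pulse rate, height, weight, BMI". For all of them, "The measurements during the treatment period (0 to 26 weeks) will be analyzed by an MMRM model with treatment, baseline value" of the response variable, then "visit, and visit by treatment interaction as fixed factors and patient as the random factor". It adds an ANCOVA of the last non-missing value and says "The ANCOVA models are the same as those used for clinical laboratory measures". SAP 5.12.5 gives that model: the last observation "will also be analyzed by an ANCOVA model with the term of treatment, baseline value of the response variable". No stratum appears in either model, and 5.12.6 names no covariance structure.

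**Protocol, tertiary route.** Section 10.3.3.3 says: "Continuous variables and the change from baseline for these variables will be analyzed either by the MMRM or ANCOVA models described in Section 10.3.3.1". Section 10.3.3.1 gives an ANCOVA with pooled country, type of basal insulin and age group, and refers to 10.3.1 for the MMRM. In 10.3.1 the MMRM "analysis will be used to analyze continuous longitudinal variables". The model there has the same three strata and an unstructured covariance, and adds the HbA1c stratum for variables other than HbA1c. Section 10.3.3.3 then leaves the details for tertiary endpoints to the SAP.

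**Protocol, safety route.** Sections 9.1.3 and 10.3.4 also list weight as a safety measure. Section 10.3.4 asks only for MMRM or ANCOVA for continuous safety variables and names no covariates.

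**The concern.** Patients are 1 to under 18 years old, and over 26 weeks many of them grow. Expected weight gain depends on age as well as on current weight: a heavy 10-year-old and a light 16-year-old can share a baseline. Baseline weight is therefore only a partial stand-in for age. A model without age group leaves part of normal growth in the residual.

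The sponsor treats age as relevant elsewhere. Age group is a randomization stratum (protocol 7.2) and a covariate in the hypoglycemia models (SAP Table ITSB.5.4). SAP 5.12.6 itself uses age bands to define abnormal blood pressure and pulse. What is at stake is the width of the interval for an exploratory weight comparison, and agreement between protocol and SAP on which model produces it.

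**Working it through.** **1. Is there another weight model in the SAP?** No. SAP 5.11.7, on exploratory objectives, covers only variables from the 7-point glucose profiles, and those keep the primary-type MMRM plus HbA1c stratum. SAP 5.2 says that other efficacy analyses use the stratification factors as noted in 5.11 and 5.12; 5.12.6 notes none. The revision history in SAP section 3 does not mention the reduced model.

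**2. Term by term**

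| Term | Protocol 10.3.1 MMRM, variables other than HbA1c | SAP 5.12.6 MMRM | SAP 5.12.6 ANCOVA |
|---|---|---|---|
| Treatment, baseline | yes | yes | yes |
| Visit, treatment by visit | yes | yes | not applicable |
| Age group | yes | no | no |
| Pooled country, basal insulin type | yes | no | no |
| HbA1c stratum | yes | no | no |
| Covariance | unstructured | not named; patient as random factor | not applicable |

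**3. Size.** The documents give no SD, power or age effect for weight change, so there is no plan figure to reproduce. Let R² be the share of residual variance, after baseline weight, that the omitted strata explain. This is an assumption, with 0.05 to 0.15 as the working range and 0 to 0.30 as the outer range.

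- SE with strata / SE without = √(1 − R²)
- Extra interval width without strata = 1/√(1 − R²) − 1
- Power without strata, for an effect that has 80% power with them (two-sided 0.05) = Φ((1.960 + 0.842) × √(1 − R²) − 1.960)

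| R² | √(1 − R²) | SE cut by adding strata | Interval wider without | Power without |
|---|---|---|---|---|
| 0 | 1.000 | 0% | 0% | 80.0% |
| 0.05 | 0.975 | 2.5% | 2.6% | 78.0% |
| 0.10 | 0.949 | 5.1% | 5.4% | 75.7% |
| 0.15 | 0.922 | 7.8% | 8.5% | 73.3% |
| 0.20 | 0.894 | 10.6% | 11.8% | 70.7% |
| 0.30 | 0.837 | 16.3% | 19.5% | 65.0% |

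The power column treats the wider SE as the estimator's real SE. Stratified randomization removes part of that real increase, so these figures are approximate.

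**4. Bias and error rate.** A simulation used 480 patients randomized 1:1 within age group, with baseline weight in the model and no true treatment effect, 3,000 runs per R².

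- Without age group, the mean treatment estimate stayed within 0.002 SD of zero: no bias.
- At R² = 0.30 the mean model SE was 0.1092 without age group and 0.0913 with it. The ratio of 1.196 agrees with 1/√0.70 = 1.195. The empirical SE without age group was 0.099, so the reported SE is too large.
- Type I error without age group was 0.053, 0.039, 0.041 and 0.032 at R² = 0, 0.10, 0.20 and 0.30. With age group it was 0.053, 0.044, 0.062 and 0.055. Monte Carlo error is about √(0.05 × 0.95/3000) = 0.004, so the direction matters more than the third digit.

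The simulation covers one 1:1 comparison and age group only, not the 2:1 comparison with LY900014+20 and not the other strata.

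**The case against.** **The protocol does not clearly require the strata for weight.** The sentence in 10.3.1 that lists three of the strata is worded for HbA1c. Weight is also a safety variable, for which 10.3.4 names no covariates, and the SAP takes that route: safety section, Safety Population, the same short ANCOVA as for laboratory tests. Section 10.3.3.3 leaves tertiary details to the SAP. This stands in part. A reader might infer a protocol violation, and the documents do not support that. Protocol 10.3.1 requires an amendment only for a principal feature and lets other changes be justified in the SAP or the clinical study report. What remains is two protocol routes to different models and no stated reason for choosing the shorter one.

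**Age is already controlled by design.** A reader might infer that chance age imbalance in the smaller LY900014+20 arm could pass for a drug effect on weight. All three arms are stratified by age group, which largely prevents this for the very factor that would be added, and the simulation found no bias. This objection stands and limits the point to precision.

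**Age group is coarse.** Its lower level runs from 1 to under 12 years, so it cannot absorb age differences within that level. This also stands. The gain could sit near the low end of the range.

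**The random patient term.** A reader might also infer a wrong error rate at Week 26 from the wording about patient as a random factor. The SAP names no covariance structure and the documents give no variances for weight by visit, so no error rate can be assigned.

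**Conclusion.** The point holds as a minor one. The SAP's weight models omit age group and the other randomization strata, the protocol's tertiary route points to models that include them, and the SAP gives no reason. The comparison remains unbiased; the interval is somewhat wider than it need be and the test somewhat conservative. Over the working range the cost is the 2.5% to 8% of the SE shown above. That rests wholly on an assumed R² and vanishes if the strata explain nothing beyond baseline weight. Weight is exploratory and outside the gatekeeping sequence, so nothing claimed on HbA1c depends on it.

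**What to change.** In SAP 5.12.6, give weight its own model statement:

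- **MMRM:** add age group. For consistency with protocol 10.3.1, also add pooled country, type of basal insulin and HbA1c stratum, and name the unstructured covariance with that section's fallback order.
- **ANCOVA of the last observation:** add the same strata.

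The other vital signs can keep the short model. If the sponsor prefers the short model for weight too, a sentence giving the reason would settle the inconsistency but forgo the precision.

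The cost is SAP wording and a small programming change before unblinding. The strata are already collected, and no data collection or sample size changes. With weight analyzed at four post-baseline visits (7, 10, 12 and 15), the unstructured matrix has 4 × 5 / 2 = 10 parameters, which is modest for a trial of about 700 patients.
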